##### **6.5.4.2 ECG Interpretation Shifts From Baseline to Worst Category**

The shift from baseline to worst ECG interpretation in safety analysis periods will be summarized by treatment group and overall as the number and percentage of subjects with normal, abnormal, and clinically significant abnormal interpretations.

Shifts will be summarized for the following safety analysis periods and populations: (1) on-DBT for treated subjects; and (2) on-DB or OL rimegepant for DB or OL rimegepant treated subjects, using DB or OL rimegepant baseline instead of baseline.

Shifts will also be summarized for the following safety analysis periods and populations by subgroup level and overall for all safety subgroups of interest described in Sections 6.1.3.3 and 6.1.3.4: on-DB or OL rimegepant for DB or OL rimegepant treated subjects, using DB or OL rimegepant baseline instead of baseline; on-OL rimegepant for OL rimegepant treated subjects, using OL rimegepant baseline instead of baseline.

##### **6.5.4.3 ECG Abnormalities**

ECG abnormalities in safety analysis periods will be summarized by treatment group and overall as the number and percentage of subjects in prespecified categories defined in the BHV3000 Core SAP.

---

Abnormalities will be summarized for the following safety analysis periods and populations: (1) on-DBT for treated subjects, (2) on-DB or OL rimegepant for DB or OL rimegepant treated subjects, and (3) follow-up for follow-up subjects.

Abnormalities will also be summarized for the following safety analysis periods and populations by subgroup level and overall for all safety subgroups of interest described in Sections 6.1.3.3 and 6.1.3.4: on-DB or OL rimegepant for DB or OL rimegepant treated subjects, using DB or OL rimegepant baseline instead of baseline; on-OL rimegepant for OL rimegepant treated subjects, using OL rimegepant baseline instead of baseline.

ECG abnormalities will be summarized together with vital sign and physical measurement abnormalities in the same tables (see Section 6.5.3.2).

### **6.5.5 Sheehan-Suicidality Tracking Scale**

The S-STIS is a prospective rating scale that contains 16 patient-reported questions and 6 clinician-reported questions to track both treatment-emergent suicidal ideation and behaviors. The S-STIS will be assessed at early termination and the following visits: screening; baseline; Weeks 2, 4, 8, and 12 of the DBT phase; Weeks 14, 16, and every 4 weeks through Week 64 of the OLE phase; and follow-up Weeks 2 and 8.

S-STIS scores are calculated as described in the BHV3000 Core SAP.

Values and changes from baseline in the self-reported S-STIS ideation subscale, behavior subscale, and total score will be summarized as continuous parameters at baseline and the worst (highest) score in safety analysis periods by treatment group and overall.

In addition, the number and percentage of subjects in the worst (highest) score change from baseline category (i.e.,  $< -1$ ,  $-1$ , no change,  $1$ ,  $> 1$ ) in safety analysis periods will also be presented by treatment group and overall for the ideation subscale, behavior subscale, and total score.

S-STIS scores, worst score changes from baseline, and worst score change categories from baseline will be summarized for the following safety analysis periods and populations: (1) on-DBT for treated subjects; (2) on-DB or OL rimegepant for DB or OL rimegepant treated subjects, using DB or OL rimegepant baseline instead of baseline; and (3) follow-up for follow-up subjects.

A by-subject listing of the S-STIS will be provided for enrolled subjects. Refer to the BHV3000 Core SAP for the listing content.

## **6.6 Outcomes Research**

Analyses will be based on as-treated treatment group.

OR (non-safety) questionnaires and rating scales are MSQoL, MIDAS, CGI-c, PoM, and SM (see Section 2.3.3). These will be assessed at early termination and the following visits: baseline

---

(MSQoL and MIDAS only), Week 12 of the DBT phase, and Weeks 24 and 64 of the OLE phase.

Measurements will be slotted into analysis periods according to assessment dates.

OR endpoints will be summarized descriptively over time. For treated subjects, measurements will be first slotted into the DBT OR and OL rimegepant OR analysis periods. Next, measurements will be slotted into analysis visit windows in these analysis periods. If a subject has multiple values in an analysis visit window in an analysis period, then the non-missing value in the analysis period closest to the target date for the visit will be used; in the case of a tie, the latest value collected will be used. Results will also be shown at the “last visit” in each phase, i.e., last non-missing measurement in the DBT OR and OL rimegepant OR analysis periods, regardless of the analysis visit window.

See Sections 6.2.5, 7.4, and 7.5 for definitions of baseline, OR analysis periods, and analysis visit windows, respectively.

By-subject listings of OR questionnaires and rating scales (i.e., MSQoL, MIDAS, CGI-c, PoM, and SM) will be provided for enrolled subjects, and will include analysis period (pre-treatment, DBT OR, OL rimegepant OR), individual components, and COVID-19 visit impact code for visits impacted by COVID-19 (see Section 9.1.5.2). Refer to the BHV3000 Core SAP for the contents of the MSQoL and MIDAS listings.

### **6.6.1 MSQoL**

See Section 6.3.2.3 for the description of the MSQoL.

### **Descriptive Analyses**

Values and changes from baseline in transformed scores for each domain will be summarized as continuous parameters (including 2-sided normal 95% CIs for mean change) by treatment group and overall for treated subjects at the following time points: baseline; Weeks 4, 12 and last visit of the DBT OR analysis period; and Weeks 24, 64, and last visit of the OL rimegepant OR analysis period.

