Procedure	Phone visit to confirm eligibility based on laboratory criteria¹	Week 14 (Day 98 ± 3 days)	Week 16 (Day 112) and 20 (Day 140) (±3 days)	Visits every 4 weeks Week 24 (Day 168) to Week 64 (Day 448) / EOT (±3 days)	2-Week Follow-up Safety Visit (14 days after EOT visit ± 2 days)	8-Week Follow-up Safety Visit (8 weeks (-2 days to +14 days) after EOT visit)
AE, SAE, and Concomitant Procedure Assessment ⁵		X	X	X	X	X ⁵
Sheehan Suicidality Tracking Scale		X	X	X	X	
Clinical Drug Supplies / Study Supplies						
Dispense Study Medication ^{1, 6}			X	X-all visits except Week 64 / EOT		
Administer Study Medication ⁷		X	X	X		
Enter Use of Study Medication in eDiary		X	X	X		
Return unused study medication to site for compliance check		X	X	X		
eDiary returned/reviewed for completeness ⁸		X	X	X		
Other Assessments						
Daily report of migraine occurrence and severity reported by subject in eDiary ⁹		X	X	X		
Migraine-Specific Quality-of-Life Questionnaire (MSQ) v 2.1				X (Weeks 24 and 64 only)		

Procedure	Phone visit to confirm eligibility based on laboratory criteria ¹	Week 14 (Day 98 ± 3 days)	Week 16 (Day 112) and 20 (Day 140) (±3 days)	Visits every 4 weeks Week 24 (Day 168) to Week 64 (Day 448) / EOT (±3 days)	2-Week Follow-up Safety Visit (14 days after EOT visit ± 2 days)	8-Week Follow-up Safety Visit (8 weeks (-2 days to +14 days) after EOT visit)
Migraine Disability Assessment (MIDAS)				X (Weeks 24 and 64 only)		

¹ Study eligibility must be confirmed by Week 12 laboratory results prior to first dose of study medication, which is dispensed at the Week 12 visit. Sites must contact subject by phone to confirm study eligibility prior to subject taking first dose.

² Concomitant medications, including prophylactic and rescue medications, taken during the Open-label, Extension Phase should be recorded in the subject’s paper diary and reviewed by study personnel at each visit. Female subjects will also record menstrual period information on the paper log which should be reviewed by study personnel at each visit.

³ Collect if treatment with concomitant medication is required for an AE or if concomitant medication is considered related to AE.

⁴ Weight, body temperature, respiratory rate, blood pressure, and heart rate will be collected at all timepoints where indicated. Sitting arterial systolic and diastolic blood pressure and radial artery pulse rate will be measured.

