### **6.3.2.3 MSQoL in the DBT Phase**

The MSQoL will be assessed at early termination and the following visits: baseline; Week 12 of the DBT phase; and Weeks 24 and 64 of the OLE phase.

The MSQoL consists of 14 items across the following 3 domains: (1) restrictive role function, (2) preventative role function and (3) emotional function. Refer to the BHV3000 Core SAP for calculating transformed domain scores and imputing missing data.

Measurements will be first selected from the on-DBT efficacy period, and then slotted into the Week 12 analysis visit window (see Week 12 of the analysis visit window for outcome research

[OR] endpoints column in Table 4). If a subject has multiple values in the analysis visit window, then the non-missing value closest to the target date for the visit will be used; in the case of a tie, the latest value collected will be used.

See Sections 6.2.5, 7.4, and 7.5 for definitions of baseline, analysis periods, and analysis visit windows, respectively.

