## Descriptive Analyses

Values and changes from baseline in the total, absenteeism, presenteeism, and item scores will be summarized as continuous parameters (including 2-sided normal 95% CIs for mean change) by treatment group and overall for treated subjects at the following time points: baseline; Week 12 and last visit of the DBT OR analysis period; and Weeks 24, 64, and last visit of the OL rimegepant OR analysis period.

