    - Post-DBT pre-OL rimegepant safety: Measurement date/time after the DBT last date + 7 days through the OL rimegepant start date/time. Note that AEs with imputed start date equal to the OL rimegepant start date are **not** part of this period. This period is used in safety listings to distinguish measurements, and to assess safety endpoints during the interim period (i.e., post-DBT pre-OL rimegepant) for interim subjects (i.e., those with > 7-day gap between DBT last date and OL rimegepant start date).
    - On-OL rimegepant safety: Measurement date/time after the OL rimegepant start date/time through the study drug last date + 7 days. Note that AEs with imputed start date equal to the OL rimegepant start date are part of this period. This period is used in safety listings to distinguish measurements, and to assess safety endpoints for OL rimegepant treated subjects in the blinded 90-Day Safety Update.
    - On-DB or OL rimegepant safety: Measurement date/time after the DB or OL rimegepant start date/time through the DB or OL rimegepant last date + 7 days. Note that AEs with imputed start date equal to the DB or OL rimegepant start date are part of this period. This period is used to assess safety endpoints on DB or OL rimegepant treatment for DB or OL rimegepant treated subjects.
    - On-treatment safety: Measurement date/time after the study drug start date/time through the study drug last date + 7 days. Note that AEs with imputed start date equal to the study drug start date are part of this period. This period is the on-DBT and on-OL rimegepant safety periods combined, and will be used to assess safety endpoints for treated subjects in the blinded 90-Day Safety Update.
-

- Follow-up safety: Measurement date after the study drug last date + 7 days. This period is used to assess safety endpoints during follow-up for follow-up subjects.
- Non-efficacy OR endpoints (see Section 6.6)
  - DBT OR: Measurement date after the DBT start date to the OL rimegepant start date. This period is used to assess OR during the DBT phase.
  - OL rimegepant OR: Measurement date after the OL rimegepant start date. This period is used to assess OR during the OLE phase.

See Section 7.3 for derived dates for determining analysis periods.

If measurement time is missing or not collected for a parameter, then the measurement date will be compared to the derived date.

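### SAP 6.6.1 lists a Week 4 MSQoL summary that no schedule supports; the only planned scores that can fall in it come from early termination

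*SAP*

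**What the plan says.** SAP 6.6.1 (MSQoL, Descriptive Analyses) plans values and changes from baseline for each domain, with 95% CIs for the mean change, by treatment group and overall in treated subjects. The double-blind time points are "baseline; Weeks 4, 12 and last visit of the DBT OR analysis period".

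The schedules do not include Week 4:

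- SAP 6.3.2.3: "The MSQoL will be assessed at early termination and the following visits: baseline; Week 12 of the DBT phase", followed by Weeks 24 and 64 of the extension.
- SAP 6.6, for all outcomes-research scales: "These will be assessed at early termination and the following visits: baseline", then "MSQoL and MIDAS only), Week 12 of the DBT phase, and Weeks 24 and 64 of the OLE phase".
- Protocol Table 1 (where the scale is called MSQ) marks it at the Baseline Visit and, after that, at Week 12 only. The Week 2 and Week 4 columns are blank.
- Protocol Table 2 marks it "X (Weeks 24 and 64 only").

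SAP 6.6.2 gives the corresponding MIDAS time points as "baseline; Week 12 and last visit of the DBT OR analysis period". SAP 6.6.3 to 6.6.5 (CGI-c, PoM, SM) list no Week 4 either.

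On assigning scores to visits, SAP 6.6 first places each score in an analysis period by its assessment date. It then says: "Next, measurements will be slotted into analysis visit windows in these analysis periods". The period is defined in SAP 7.4: "DBT OR: Measurement date after the DBT start date to the OL rimegepant start date". SAP Table 4 covers outcomes-research scores and sets the Week 4 window at study days 22 to 42.

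**The concern.** A time point with no scheduled assessment might be thought harmless, on the view that the row will simply be blank. Under the SAP's own rules it need not be. The SAP plans an MSQoL at early termination, and visits are assigned by date, not by visit name. A subject who stops and completes the questionnaire between study days 22 and 42 is therefore counted at Week 4, while a subject who continues has no planned score there.

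The table would then show, for each arm and each of the three domains, a mean change with a confidence interval under a Week 4 label, next to a Week 12 row made up mainly of subjects who stayed. A reader would naturally take the two rows as an early time course of quality of life. The Week 4 row would in fact describe a group selected by leaving, possibly for different reasons in each arm.

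**Working it through.** The plan states no figure to reproduce here. The check is which planned MSQoL assessments can carry a date inside the Week 4 window.

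**Inputs**

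- Table 4 windows in study days: Week 2 is 1 to 21, Week 4 is 22 to 42, Week 8 is 43 to 70, Week 12 is 71 to 91, Week 24 is 155 to 182, Week 64 is 435 to 462.
- Protocol visit days: Week 12 is Day 84 with a window of +3 days (84 to 87); Week 24 is Day 168 ± 3 (165 to 171); Week 64 is Day 448 ± 3 (445 to 451).
- Baseline (SAP 6.2.5): the last value on or before the start of study drug.
- Double-blind outcomes-research period (SAP 7.4): from after the first double-blind dose to the start of open-label rimegepant, with no cut-off tied to the last dose.

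**Assigning each planned assessment**

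| Planned assessment | Study days | Table 4 row |
|---|---|---|
| Baseline | on or before drug start | baseline, outside the period |
| Week 12 | 84 to 87 | Week 12 |
| Week 24 | 165 to 171 | Week 24 |
| Week 64 | 445 to 451 | Week 64 |
| Early termination (SAP only) | any day | whichever window the date falls in, including Week 4 |

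The earliest scheduled post-baseline score, at Day 84, comes 84 − 42 = 42 days after the Week 4 window closes. Visit-window slippage of +3 days cannot bridge that. Protocol visit days are nominally counted from the Baseline Visit and Table 4 days from the first dose, but a first dose would have to be delayed by about six weeks to change the result. Early termination is therefore the only planned source for the row.

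**Is the row a deliberate early-termination summary?** It does not look like one. Early-termination scores from days 1 to 21 and 43 to 70 would fall in the Week 2 and Week 8 windows, and SAP 6.6.1 lists neither. Nothing explains why only days 22 to 42 should be shown.

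**Is anything lost by deleting it?** No. SAP 6.6 defines the last-visit row as the last non-missing score in the period whatever its window. An early terminator's score is already counted there.

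**How many subjects?** The documents do not say. They give no early-termination counts by week and no return rate for the questionnaire at that visit.

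**The case against.** Four points can be made on the other side.

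*The row may be empty.* Early-termination MSQoL appears only in the SAP. Protocol Table 2 restricts the questionnaire to Weeks 24 and 64, whereas its rows for physical examination, safety laboratory tests, lipids and ECG name Week 64 together with EOT. Protocol 4.3.4 does not mention the questionnaire among the end-of-treatment procedures. Sites following the protocol strictly might collect none at an early exit. This stands. The time point would then have no planned data at all, and the same correction applies.

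*Continuing subjects are not strictly excluded.* An unscheduled or mistimed form dated days 22 to 42 would also be placed in the row. This stands too. A reader might infer that no continuing subject can contribute, but that is true only of planned assessments.

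*The number affected is unknown.* It is tempting to estimate it from two planning figures: 370 of 400 per arm in the efficacy set, or 675 of 800 entering the extension. Neither is a dropout figure. The efficacy set turns on treatment and on having at least 14 diary days in the observation period and in at least one double-blind month, so a subject who stops around days 22 to 42 may already qualify through Month 1. Non-entry to the extension includes subjects who completed 12 weeks and did not continue (SAP 6.2.3.3) and those with unacceptable Week 12 laboratory results (Protocol 4.1). The documents support no per-arm count and no standard-error comparison.

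*The consequence is small.* The table is descriptive, as-treated and exploratory. Protocol 9.1 includes n among the summary statistics, so a thin row should be visible. This limits the weight of the point, but n alone does not tell a reader that those subjects had left.

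The table shells are in separate documents, so what was actually printed cannot be checked from the protocol and SAP.

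**Conclusion.** Wrong as written, and minor: an internal inconsistency in an exploratory descriptive table. SAP 6.6.1 asks for an MSQoL summary at a visit where neither document schedules the scale. Followed literally, the SAP fills that row with early-termination scores from study days 22 to 42, if those scores are collected. Some may be off drug, since the period has no last-dose limit and SAP 2.3 uses a treatment-policy strategy for outcomes research. Any mean change and interval in the row would describe a selected group and not an on-study time course.

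A reader might infer that the tested MSQoL endpoint is compromised. It is not. The hierarchical test uses the restrictive role function change at Week 12 in evaluable mITT subjects (SAP 6.1.2 and 6.3.2.3), and the ad hoc as-treated comparison in SAP 6.6.1 also uses Week 12.

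The conclusion assumes that Table 4 is applied as SAP 6.6 directs and that no Week 4 assessment was intended. It does not depend on how many subjects would fall in the row.

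**What to change.** In SAP 6.6.1, change the double-blind time points to match SAP 6.6.2: "baseline; Week 12 and last visit of the DBT OR analysis period". Leave the extension time points as they are. Early-termination scores remain in the last-visit row.

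The Revision History says version 10.0 was issued after the final database lock, so the Week 12 table may already exist. In that case drop the row, or add a footnote stating that MSQoL was not scheduled at Week 4 and saying which subjects contribute to it. If a Week 4 assessment was in fact intended, Protocol Table 1, SAP 6.3.2.3 and SAP 6.6 must be reconciled with SAP 6.6.1.

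The cost is one time point in the text and one row (per domain) in a table shell, with no new data and no change to any test.

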### **Treatment Group Comparisons**

This adhoc analysis was added to the CSR.

Analyses are based on treated subjects with MSQoL domain scores at both baseline and Week 12 of the DBT OR analysis period. For each MSQoL domain, the score change from baseline at Week 12 between treatment groups is compared using the same methodology as described in Section 6.3.2.3.

### **6.6.2 MIDAS**

See Section 6.3.2.4 for the description of the MIDAS.

---

## Descriptive Analyses

Values and changes from baseline in the total, absenteeism, presenteeism, and item scores will be summarized as continuous parameters (including 2-sided normal 95% CIs for mean change) by treatment group and overall for treated subjects at the following time points: baseline; Week 12 and last visit of the DBT OR analysis period; and Weeks 24, 64, and last visit of the OL rimegepant OR analysis period.

## Treatment Group Comparisons

This adhoc analysis was added to the CSR.

Analyses are based on treated subjects with MIDAS scores at both baseline and Week 12 of the DBT OR analysis period. For each MIDAS score (total, absenteeism, presenteeism), the score change from baseline at Week 12 between treatment groups is compared using the same methodology as described Section 6.3.2.4.

### 6.6.3 CGI-c Scale

The CGI-c is an observer-rated 7-point scale that measures patient total improvement relative to the investigator's past experience with other patients with the same diagnosis, with or without collateral information. The 7 improvement categories are: very much improved, much improved, minimally improved, no change, minimally worse, much worse, and very much worse.

The number and percentage of treated subjects in each category (including combined categories) will be presented by treatment group and overall at the following time points: Week 12 and last visit of the DBT OR analysis period; and Weeks 24, 64, and last visit of the OL rimegepant OR analysis period. Percentages for categories will be based on subjects with non-missing data at each visit along with 2-sided Agresti-Coull 95% CIs for each percentage. Refer to the BHV3000 Core SAP for combined categories.

### 6.6.4 PoM

The PoM is a 5-point rating scale that measures the patient's preference of study medication to previous medications to treat migraine pain using the eDiary. The 5 preference categories are: much better, I prefer this medication; slightly better than the previous medication; about the same as the previous medication; slightly worse than the previous medication; and much worse, I prefer my previous medication.

The number and percentage of treated subjects with PoM data and in each category (including combined categories) will be presented by treatment group and overall at the following time points: Week 12 and last visit of the DBT OR analysis period; and Weeks 24, 64 and last visit of the OL rimegepant OR analysis period. Percentages for categories will be based on subjects with non-missing data at each visit, along with 2-sided Agresti-Coull 95% CIs for each percentage. Refer to the BHV3000 Core SAP for combined categories.

---

### **6.6.5 SM**

The SM is a 7-point rating scale that measures the patient's satisfaction with study medication to treat migraines using the eDiary. The 7 satisfaction categories are: completely satisfied, could not be better; very satisfied; somewhat satisfied; neither satisfied nor dissatisfied; somewhat dissatisfied; very dissatisfied; and completely dissatisfied, could not be worse.

The number and percentage of treated subjects with survey data in each category (including combined categories) will be presented by treatment group and overall at the following time points: Week 12 and last visit of the DBT OR analysis period; and Weeks 24, 64, and last visit of the OL rimegepant OR analysis period. Percentages for categories will be based on subjects with non-missing data at each visit along with 2-sided Agresti-Coull 95% CIs for each percentage. Refer to the BHV3000 Core SAP for combined categories.

